### 12 STATISTICAL CONSIDERATIONS

# 12.1 Study Hypotheses

**Primary Objective:** To compare children's physiological anxiety (EDA - primary outcome) during the dental cleaning in SADE vs. RDE.

**Hypothesis 1:** Children will exhibit less physiological anxiety (SCL and NS-SCR frequency) during routine dental care in the SADE condition compared to the RDE.

**Secondary Objective 2:** To compare children's negative behavioral responses (behavioral distress, perception of pain, sensory discomfort - secondary outcomes) during dental cleanings in SADE vs. RDE.

**Hypothesis 2:** Children will exhibit fewer negative behavioral responses during routine dental care in the SADE condition compared to the RDE.

**Secondary Objective 3:** To test the degree to which physiological anxiety mediates the SADE intervention's effects on children's negative behavioral responses.

**Hypothesis 3:** Physiological anxiety mediates the effect of the intervention in decreasing child negative behavioral responses.

**Secondary Objective 4:** To test the degree to which specific child characteristics moderate the SADE intervention's effects on children's physiological and negative behavioral responses during dental cleaning.

**Hypothesis 4:** The magnitude of physiological and negative behavioral response change in the SADE, relative to the RDE, will be greater in children with ASD with increased sensory over-responsivity, high dental anxiety, greater ASD severity, lower IQ, and/or younger age.

**Secondary Objective 5:** To compare the SADE intervention to the RDE on quality of care, cost-effectiveness, and potential cost savings of dental cleaning.

**Hypothesis 5a:** The SADE intervention, compared to the RDE, is cost-effective and results in decreased overall costs.

**Hypothesis 5b:** The SADE intervention, compared to the RDE, results in improved quality of care as evidenced by thoroughness of dental cleaning.

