## Secondary Objective 5: Hypotheses 5a & 5b

Hypotheses 5a and 5b are similar, examining the environment difference on the costs and quality of care. The general model is presented below. Quality of care will be determined by scoring of pre- vs. post- intra-oral photographs on the OHI-S and Plaque Index measures. Health care costs are defined as personnel time burden, including direct costs of the intervention (e.g., training, materials, overhead, and direct patient care). The cost-effectiveness of the SADE intervention will be represented in the form of an incremental cost-effectiveness ratio of the cost (C) relative to the quality of care (E):  $(C_{SADE} - C_{RDE})/(E_{SADE} - E_{RDE})$ .

Hyp 5: Cost or Quality = 
$$B_0 + B_1*Environment$$

These models are paired and will involve paired t-tests or non-parametric corollary for continuous outcomes if the outcome is normal or non-normally distributed, respectively. For dichotomous outcomes (e.g., need for sedation), McNemar's test will be used to examined differences in need for the paired observations.

Cost Effectiveness Analysis. In assessment of medical interventions, cost-effectiveness evaluations become increasingly relevant. Using this evaluation approach and the comparative intervention RDE as the reference standard, the cost-effectiveness of the SADE intervention will be represented in the form of an incremental cost-effectiveness ratio as:  $(C_1 - C_0)/(E_1 - E_0)$ , where the subscript 1 refers to the SADE intervention arm and the subscript 0 refers to the RDE comparative arm.  $C_1$  represents the average net cost of implementing the intervention;  $C_0$  represents the average net cost of the RDE comparative arm;  $E_1$  represents the quality of care associated with the SADE intervention; and  $E_0$  represents the quality of care associated with RDE. We will consider alternative effectiveness outcomes.

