We will use alternative measures of effectiveness in conducting our economic evaluation of the intervention. We will also combine several of the effectiveness scales into a measure of dental performance using structural equations models with unobservable dental health status as a latent variable in a multiple indicators, multiple causes framework. In this approach, all structural measures of dental treatment including patient functional status and patient outcome measures will be used as health status indicators, whereas clinical, environmental, and background characteristics will serve as causal factors in explaining dental health status changes. We will compute confidence intervals for the cost-effectiveness ratios using bootstrapping and develop cost-effectiveness acceptance curves. In this approach, all structural measures of dental treatment including patient functional status and patient outcome measures will be used as health status indicators, whereas clinical, environmental, and background characteristics will serve as causal factors in explaining dental health status changes.

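### The ICER and its bootstrap interval cannot be read as a cost-effectiveness summary if SADE proves cheaper and better, which is what Hypotheses 5a and 5b predict

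*Combined protocol and SAP*

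**What the plan says.** Section 12.1 gives the two hypotheses. Hypothesis 5a reads: "The SADE intervention, compared to the RDE, is cost-effective and results in decreased overall costs". Hypothesis 5b reads: "The SADE intervention, compared to the RDE, results in improved quality of care as evidenced by thoroughness of dental cleaning".

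Section 12.4, under Secondary Objective 5, says that the cost-effectiveness of SADE "will be represented in the form of an incremental cost-effectiveness ratio of the cost (C) relative to the quality of care" (E). The formula is the SADE-minus-RDE cost difference over the SADE-minus-RDE quality difference. The paragraph on cost-effectiveness analysis repeats the formula and defines the SADE effect term as what "represents the quality of care associated with the SADE intervention". On where that term comes from: "Quality of care will be determined by scoring of pre- vs. post- intra-oral photographs on the OHI-S and Plaque Index measures". The direction in which E is scored is not given.

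On uncertainty: "We will compute confidence intervals for the cost-effectiveness ratios using bootstrapping and develop cost-effectiveness acceptance curves". The type of bootstrap interval is not named. The same section also plans separate paired comparisons of cost and of quality (paired t-test or a non-parametric counterpart, and McNemar's test for dichotomous outcomes).

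There is no rule for a negative ratio or for bootstrap replicates that fall in different quadrants. There is also no dominance statement, net-benefit summary or willingness-to-pay range.

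**The concern.** An ICER has a price-per-unit meaning only when there is a trade-off: more cost for more benefit, or less cost for less benefit. Hypotheses 5a and 5b together predict no trade-off. In that quadrant the ratio is negative. A larger saving pushes it away from zero and a larger quality gain pulls it back, so neither a larger nor a smaller ratio means a better result. The opposite quadrant, where SADE loses on both counts, yields the same negative numbers. A bootstrap interval inherits the defect, because its two limits are not a worse case and a better case.

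At stake is how the cost-effectiveness part of Hypothesis 5a is reported. A reader given only the ICER and its interval could not tell a strong result from a weak one, or a win from a loss.

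**Working it through.** **Inputs.** From Section 12.1: cost difference ΔC < 0 (5a) and quality difference ΔE > 0 (5b). From Section 12.4: ICER = ΔC/ΔE. From Section 12.2: 165 children with both visits and a detectable within-child d of 0.22. The documents give no expected cost or quality difference, no standard deviations and no willingness-to-pay λ. All such values below are assumptions.

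**1. The plan's own figure.** The documents state no figure for the ICER, so the only one to reproduce is the detectable effect. For paired data, d = (1.960 + 0.842)/√165 = 0.218, which matches 0.22 at two-sided 0.05 (one-sided 0.025) and 80% power. It was not derived for plaque or cost and serves here only as a scale.

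**2. Sign and ranking.** Net benefit is NB = λ·ΔE − ΔC. Assumed dollar and quality values, with λ = 100:

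| ΔC | ΔE | ICER | NB | Reading |
|---|---|---|---|---|
| −20 | +0.1 | −200 | 10 + 20 = 30 | cheaper, better |
| −20 | +0.2 | −100 | 20 + 20 = 40 | cheaper, better by more |
| −40 | +0.2 | −200 | 20 + 40 = 60 | cheaper by more, better by more |
| +20 | −0.1 | −200 | −10 − 20 = −30 | dearer, worse |
| −20 | −0.1 | +200 | −10 + 20 = 10 | trade-off |
| +20 | +0.1 | +200 | 10 − 20 = −10 | trade-off |

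Three quite different results share −200, one of them a loss on both counts. The second row beats the first but has a ratio nearer zero. The last two rows show that even a positive ratio needs its quadrant named.

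**3. Behaviour of the interval.** Bootstrap of 165 pairs, 20,000 resamples, differences in standard-deviation units, uncorrelated. The percentile interval is an assumption. The last column gives the range over λ = 0, 0.5, 1 and 2 in the same units.

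| ΔC, ΔE | ICER | 95% interval | Replicates cheaper and better | P(NB > 0) |
|---|---|---|---|---|
| −0.44, +0.44 | −1.0 | −1.67 to −0.59 | 100% | 1.000 |
| −0.22, +0.22 | −1.0 | −3.37 to −0.27 | 99.5% | 0.998 to 1.000 |
| −0.22, +0.11 | −2.0 | −18.88 to 14.73 | 91.7% | 0.993 to 0.999 |
| −0.11, +0.11 | −1.0 | −10.11 to 7.12 | 84.8% | 0.922 to 0.976 |

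Three rows share an ICER of −1.0, although at λ = 1 their net benefits are 0.88, 0.44 and 0.22. In the third row the interval spans zero widely while net benefit is almost surely positive. In the first two the interval stays negative, but its limits still do not order better and worse.

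**4. How often the denominator changes sign.** If the true quality difference is k standard errors from zero, the share of replicates with the wrong sign, averaged over trials, is Φ(−k/√2): 36% at k = 0.5, 24% at k = 1 and 8% at k = 2. At d = 0.22 with 165 pairs, k = 0.22 × √165 = 2.83 and the share is Φ(−2.00), about 2%.

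**The case against.** The strongest reply is that the plan is not left without a usable summary. The sentence that promises the interval also promises acceptability curves. Such a curve is the probability of positive net benefit as λ varies, and it is valid in every quadrant. The separate paired tests would show the sign of each difference, so a win and a loss would not in practice be confused. This stands. It leaves open which λ range the curve covers and how a negative ratio or mixed-quadrant replicates are reported.

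A reader might infer more than the documents support:

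- That the plan cannot support any claim of cost-effectiveness. That is true of the ICER alone, not of the plan.
- That the denominator lies near zero because both cleanings aim to remove plaque. No plaque difference or standard deviation is given, so this is conjecture. At the plan's d of 0.22, taken as an assumption, only about 2% of replicates change sign.
- That the interval is falsely precise or covers badly. The plan names no percentile interval. If one is used (independent normal differences, simulated), coverage is 94–99% once the quality difference is at least 0.5 standard errors, and drops to about 81–95% only at 0.2. Mixed-quadrant intervals come out very wide, not narrow.

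It can also be said that SADE may not be cheaper, since Section 12.4 counts training and materials as costs and Section 6.1 mentions about 15 minutes to set up or remove the equipment. That makes a trade-off possible, but it is one more reason to say in advance how each quadrant will be reported.

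**Conclusion.** The concern holds for the ICER and its bootstrap interval as the headline cost-effectiveness summary. If 5a and 5b are both true and higher E means better quality, the ratio is negative, can equal that of a dearer-and-worse result, and has limits that cannot be read in order. This follows from the formula and the hypotheses and needs no assumed magnitude. The dollar, quality and standardised values above only illustrate it.

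The negative sign depends on the direction of E. The label quality of care implies that higher is better, but if E were a raw post-cleaning plaque or OHI-S score, where lower is better, a cheaper-and-better result would give a positive ratio that looks like a trade-off. The scoring direction therefore needs to be stated in either case.

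The harm is to interpretation, within one secondary objective. The primary analysis, the sample size, the data collected, the paired tests and the acceptability curves are unaffected. Severity is minor, and the change is a cheap improvement.

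**What to change.** Amend Secondary Objective 5 in Section 12.4 as follows:

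- State that E is scored so that higher means better quality.
- Make incremental net benefit, λ·(E_SADE − E_RDE) − (C_SADE − C_RDE), the reported statistic over a pre-stated range of λ. Give it a bootstrap interval that resamples children, so that each child's two visits stay together.
- Keep the acceptability curve, over the same range of λ.
- Give the cost difference and the quality difference, each with an interval.
- Quote an ICER with an interval only when cost and quality differ in the same direction, and name the quadrant. Otherwise report dominant or dominated, with the share of bootstrap replicates in each quadrant.

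This costs SAP wording only and uses the same data and the same bootstrap. The one real burden is choosing a λ range for a plaque-based scale with no stated money value. The planned acceptability curve needs that range in any case.

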# 13 SOURCE DOCUMENTS AND ACCESS TO SOURCE DATA/DOCUMENTS

The study staff will maintain appropriate medical and research records for this study, in compliance with ICH E6, Section 4.9 and regulatory and institutional requirements for the protection of confidentiality of subjects. Study staff will permit authorized representatives of NIDCR and regulatory agencies to examine (and when required by applicable law, to copy) research records for the purposes of quality assurance reviews, audits, and evaluation of the study safety, progress and data validity.

### 14 QUALITY CONTROL AND QUALITY ASSURANCE

This study has a comprehensive manual of procedures (MOP), including standard operating procedures (SOP) for each study-related task.

The research team will meet every other week to review structure and processes, identify any errors, and determine ways to prevent future errors. [name] [name] (Co-I), who is responsible for implementation of staff training and quality assurance, will meet with the PI and Project Specialist on alternate weeks, and as needed in the interim times. When errors occur, we will consider the following: Are there adequate written procedures? Were the procedures followed? Was training done? Was it adequate? Is work being monitored? Are individual roles and responsibilities clear and defined? Clarifications and additions will be made as needed.

All hard-copy documents will be visually checked by a member of the research team after completion and again prior to filing to ensure 100% completion of forms. All forms (parent-, child-, dentist-, and researcher-report forms) will be entered into our database and visually data checked to ensure quality and accuracy of data reporting; if there are more than 4-6 errors per 1,000 entries, we will re-train data entry staff and check the subsequent 1,000 entries. If again there are more than 4-6 errors per 1,000 entries we will switch to double data entry in the Café Database. Additionally, 25% of all video-recordings and EDA recordings will be double-coded to ensure proper inter-rater reliability and adherence to scoring protocols.

[name] [name] (Co-I) will be responsible for addressing quality assurance issues by asking detailed questions of research members collecting data and visually inspecting one of every 10 child's forms. Quality assurance/quality control tasks regarding data entry will include visual data checking by one independent research assistant. Following a noted discrepancy, the Project Coordinator, Research Assistant (OTD Resident), PhD Student, Project Specialist, or [name] will check the source document to resolve disagreement, determine how the error was made (e.g., mis-entry, illegible handwriting, etc), and the correct data will be input into the Café database. [name] will then review data entry processes with the data entry research team member who entered the data incorrectly, ensuring that no questions or confusion exists in regard to his/her job responsibilities.

All training will be conducted by [name]. Staff will complete mock administrations of all forms, including consent and assent. Video-recording training will occur on-site at CHLA regarding camera placement and goals of recordings. Video-recording coding training (how to code the CDBRS) will occur at USC. The training video will be viewed, questions will be asked of [name], and a minimum of 10 videos will be viewed and scored, ensuring inter-rater reliability with [name], with a minimum of 85% agreement. Training in the use of electrodermal equipment will include practice set-up and recording of volunteer students and other research team members. Training to understand psychophysiological concepts and administer and score EDA recordings will include five hour-long lectures and one hour-long laboratory activity by [name] (Co-investigator and EDA expert) followed by practice scoring, supervised by [name]. At least 10 recordings coded independently by the team member with a minimum of 85% agreement with [name] will be required, ensuring inter-rater reliability on this measure. [name] will also train all data entry staff on the use of the SADE database in the Café system, originally created for the R34 and modified for the U01.

## 15 ETHICS/PROTECTION OF HUMAN SUBJECTS

### 15.1 Ethical Standard

The investigator will ensure that this study is conducted in full conformity with the principles set forth in The Belmont Report: Ethical Principles and Guidelines for the Protection of Human Subjects of Research, as drafted by the US National Commission for the Protection of Human Subjects of Biomedical and Behavioral Research (April 18, 1979) and codified in 45 CFR Part 46 and/or the ICH E6; 62 Federal Regulations 25691 (1997).

### 15.2 Institutional Review Board

The protocol, informed consent form(s), recruitment materials, and all subject materials will be submitted to the IRB for review and approval. Approval of the protocol, consent form, and assent form will be obtained before any subject is enrolled. Any amendment to the protocol will require review and approval by the IRB before the changes are implemented in the study.

*Note.* This study will obtain dual approval, as done in the R34 Pilot Study, from Children's Hospital Los Angeles IRB (the Committee on Clinical Investigations) as well as the University of Southern California's IRB (Health Sciences Review Board).

#### 15.3 Informed Consent Process

Informed consent is a process that is initiated prior to the individual agreeing to participate in the study and continues throughout study participation. Extensive discussion of risks and possible benefits of study participation will be provided to subjects and their families, if applicable. A consent form describing in detail the study procedures and risks will be given to the subject. Consent forms will be IRB-approved, and the subject will be required to read and review the document or have the document read to him or her. The investigator or designee will explain the research study to the subject and answer any questions that may arise. In order to assure that the subject understands, the investigator will ask the subject to verbally summarize what they are going to do. The subject will sign the informed consent document prior to any study-related assessments or procedures. Subjects will be given the opportunity to discuss the study with their surrogates or think about it prior to agreeing to participate. They may withdraw consent at any time throughout the course of the study. The rights and welfare of the subjects will be protected by emphasizing to them that the quality of their clinical care will not be adversely affected if they decline to participate in this study.

Study assent forms will be used for children with ASD when appropriate. The study will be verbally described to the child and the child subject will be provided with a simplified form (assent) providing the details of the study intervention, study procedures, and potential risks. In order to assure that the child understands, the investigator will ask the child to verbally summarize what they are going to do. The child will then sign and date the assent. For those subjects who are unable to give assent based on their cognitive abilities, the subject will be informed about the trial to the extent compatible with the subject's understanding.

The original signed and dated consent/assent forms will be retained by the study staff. However, a second original of each form will be given to subjects for their records, and a copy of each form will be placed in the child's CHLA dental chart.

Additionally, as this study will recruit both English- and Spanish-speaking families, professionally translated consent and assent documents will be available to parents and child. Additionally, appropriate study team members who are fluent in Spanish, will conduct the consent and assent procedures.

The consent process will be documented in the clinical and research record. The NIDCR Informed Consent and Assent Documentation Checklist will be reviewed to be sure all aspects are included in the Consent (see Appendix L in MOP). The two documents, "Documenting the Consent Process" and "Suggestions for Consenting/Assenting Research Subjects/Participants" will be used as training tools and serve as a reminder of the tasks associated with adequate consent practices and documentation.

## 15.4 Exclusion of Women, Minorities, and Children (Special Populations)

Our study excludes children younger than 6.0 years and older than 12.11 years, as well as participants (parents) who do not fluently speak English or Spanish.

Age. Research indicates that younger age is associated with the presence of uncooperative behaviors in the dental operatory in children with ASD. Additionally, this project provides a conceptual replication and extension of Shapiro et al.'s previous work with children with developmental disabilities (other than ASD) in Israel; in this study a similar age-range was used.

Language. Participants will be recruited primarily from CHLA and LAUSD, which provides services to an ethnically diverse population, with approximately 60-70% Hispanic/Latino. Therefore, we anticipate that the majority of our sample will be either English- or Spanish-speaking. Additionally, some of the tools we will be using have only been validated in English and Spanish.

## 15.5 Subject Confidentiality

Subject confidentiality is strictly held in trust by the investigators, study staff, and the sponsor(s) and their agents. This confidentiality is extended to cover testing of biological samples and genetic tests in addition to any study information relating to subjects.

The study protocol, documentation, data, and all other information generated will be held in strict confidence. Only the Principal Investigator, [name] [name] (Co-I and responsible for training and quality assurance), the Project Specialist, and members of the research staff collecting or participating in data entry will have access to study records (e.g., forms, video-recordings, EDA recordings, etc.). No information concerning the study or the data will be released to any unauthorized third party without prior written approval of the Principal Investigator.

The study monitor, representatives of the NIDCR, and IRB representatives may inspect all study documents and records required to be maintained by the investigator, including but not limited to, all CRFs, video-recordings, intra-oral photographs, and EDA recordings for the study subjects. The study site (office containing CRF, etc. storage, not CHLA where intervention is performed) will permit access to such records.

